7.1 Information to be collected on screening failures

If a patient is screened but not randomized, only demographic information and the Screening Log entry with the primary reason for non-randomization will be completed.

7.2 Patient demographics/other baseline characteristics/medical history

Demographics and baseline characteristics are to be collected on all patients including age, sex, race, height and weight.

Relevant specific medical history will be captured especially the information highlighted below:

□ Concurrent injuries concerning the lower and upper limbs.

7.3 Assessment of injury

The size of injury is measured by the Investigator. The size must be at least 25 cm² and at most 120 cm^2 on the basis of the largest perpendicular diameters. The localization should also be documented in detail in the patient CRF.

7.4 Treatment exposure and compliance

The patient will record in the diary the date and time of every application of study drug.

The patient will return the study drug (used or unused) at the last visit. The number of patches used and unused will be recorded in the accountability form in the CRF.

The Investigator or designee will store the study drugs until the monitor arranges for their return. The Investigator must not destroy any drug. The monitor will check the number of patches at every monitoring visit to verify the drug accountability details entered in the CRF.

7.5 Efficacy

7.5.1 Clinic visit efficacy assessments

The following chronological sequence will be observed for the efficacy assessments below:

- 1. Pain at rest/spontaneous pain (PAR)
- 2. Pain-on-movement (POM)

The global assessments may be completed at any time during the assessment process.

Pain-at-rest (PAR)

PAR will be measured at injured site in mm using a 100 mm VAS at Visits 1-7

The patient will then answer the question:

"How would you describe the pain in the injured area at rest?"

The patient will draw a perpendicular line on a 100 mm Visual Analogue Scale (VAS) with a pen between 0 = "no pain" and 100 = "Extreme pain" to reflect the pain intensity at rest.

|-----|

No pain

Extreme Pain

Pain-on-movement (POM)

POM will be assessed at the study center at Visits 1–7 using a 100 mm VAS. The result will be written in the CRF.

To standardize the procedure for the assessment of pain-on-movement a special movement should be performed by the patient, either for the upper limb or the lower limb depending on which limb is injured.

□ To assess pain-on-movement of the upper limb, the patient will be instructed to grab a 3 kg bar with the hand of the injured arm, slowly lift the bar by bowing the elbow from the 0 position to a 160 degree position and then slowly move the arm back to the starting position.

Figure 7.5.1: Exercise to assess pain-on-movement of the upper limbs

The patient will then answer the question:

"How would you describe the pain in the injured area while you were moving your arm?"

□ To assess the pain-on-movement of the lower limb, the patient will be instructed to slowly walk 5 steps on an even surface. The patient must initiate the walk with the injured limb (i.e. take 3 of the 5 steps with the injured limb).

The patient will then answer the question:

"How would you describe the pain in the injured area while you were walking?"

The patient will draw a perpendicular line on a 100 mm Visual Analogue Scale (VAS) with a pen between 0 = "no pain" and 100 = "Extreme pain" to reflect the pain intensity during movement.

|-----|

No pain

Extreme Pain

Global efficacy assessments

The global efficacy assessments are evaluated by the patient at Visits 4, 5 and 7 as the response to following questions:

- □ "Considering all the ways this treatment has affected you since you started in the study, how well are you doing?" It is assessed on the following 5-point Likert scale:
- 0 = very good
- 1 = good
- 2 = fair
- 3 = poor
- 4 =very poor.
- □ "How do you rate this medication as a treatment for your soft tissue injury/contusion?" It is assessed on the following 5-point Likert scale:

0=excellent

1=very good

2=good

3=fair

4=poor

The global efficacy assessments are evaluated by the Investigator at Visits 4, 5 and 7 as the response to following questions:

• "Considering all the ways this treatment has affected the patient since he/she started in the study, how well is he/she doing?" It is assessed on the following 5-point Likert scale:

0 = very good

1 = good

2 = fair

3 = poor

4 = very poor.

Adhesive power of the patch

The adhesive power of the patch will be measured by a 5 point numerical scale ($0=\geq 90\%$ adhered / $1=\geq 75\%$ to <90% adhered / $2=\geq 50\%$ to <75% adhered / 3=>0% to <50% adhered / 4=completely detached) at every visit except V1.

Assessment of local tolerability of the patch

Local tolerability will be assessed by the Investigator according to the following numerical scale:

Score	Definition	
0	No evidence of irritation	
1	Minimal erythema, barely perceptible	
2	Definite erythema, readily visible, minimal edema or minimal papular response	
3	Erythema and papules	
4	Definite edema	
5	Erythema, edema and papules	
6	Vesicular eruption	
7	Strong reaction spreading beyond test site	

Use of rescue medication

Each use of rescue medication will be recorded in the CRF or in the diary. The Investigator/ the patient will record the date and time, the number of tablets taken and the reason for rescue (blunt trauma pain or other).

Resolution of soft tissue injury/contusion

Resolution of soft tissue injury/contusion is assessed by the Investigator at the final study visit. Time to resolution is the time of last application of study medication because the soft tissue injury/contusion has resolved. This is based on the record of applications of study medication and the assessments of efficacy.

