Use of systemic or topical NSAIDs, analgesics (other than paracetamol), opioids, corticosteroids (except for topical treatment of bronchial asthma), heparin, or psychotropic agents, as well as the use of adhesive and fixing tapes and casts that would jeopardize the assessment of the primary variable (pain on movement).

3. Other treatments

. Ultrasound, physical therapy and acupuncture will not be allowed

Dosage Patients will be randomly assigned to one of the following treatment arms in a ratio of 1:1.

A: Esflurbiprofen Hydrogel Patch applied once per day to the affected injury site

B: Placebo patch applied once per day to the affected injury site

The dose regimen is a single hydrogel patch (investigational drug) applied topically to the injured site once a day for 7 days. The hydrogel patch should be positioned directly over the injury site and marked with a water-resistant pen to ensure the patch is applied at the same site throughout the study. The placebo patch (placebo) is identical in composition to the Esflurbiprofen 165 mg Hydrogel Patch, without the active ingredient. Placebo is applied as described for the investigational drug. Both patients and investigators will be blinded to study treatment. If the hydrogel patch begins to peel-off (>10% of the total surface), the edges of the topical system may be pressed down. If problems with adhesion persist, patients may overlay the topical systems applied to ankles, knees, or elbows). The mesh netting sleeve must allow air to pass through and not be occlusive (non-breathable)

Teikoku Chemical Co. Clinical Study Protocol	Ltd : TK-254R-0201	Confidential Final Version 3.0	Page 14
No. of Visits	A total of 7 visits		
Visit Schedule	 Visit 1 of Visit 2 of Visit 3 of Visit 4 of Visit 5 of Visit 6 of Visit 7 of 	n Day 1 (enrollment) n Day 1/2, depending on am/ n Day 2 (24 hours) n Day 3 (48 hours) n Day 4 (72 hours) n Day 5 (96 hours) n Day 8 (168 hours).	pm enrollment (12 hours)
Assessments	Efficacy will be a	assessed based on the followi	ng:
	 Primary assessme Pain-on-move standardized = 12, 24, 48, 72 Secondary assess AUC over time 	ent: cment (POM) measured by 10 movements as described in S d, 96 and 168 hours ments: me between baseline and the	00 mm VAS [performing ection 7.5.1] at baseline, first 12, 24, 48, 72, 96 and

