3.2 Secondary objective

To assess the safety of Esflurbiprofen Hydrogel Patch compared with placebo applied once a day for up to seven days.

4 Study design

This is a Phase II randomized, double-blind, 2-arm (1:1) (stratified by center and subgroup), multi-center, placebo-controlled, parallel group study of the efficacy and safety of Esflurbiprofen Hydrogel Patch applied once a day for up to 8 days (maximum of 7 patches) to treat acute blunt, soft tissue injuries of the limbs.

To qualify, patients must experience acute blunt, soft tissue injuries of the limbs. Patients should be randomized as soon as possible after the injury. Anticipated time from injury until initial treatment should not exceed 6 hours.

In order to ensure at least 90 evaluable patients per group, up to 200 patients (100 in each group)

Approximately 200 patients suffering from acute blunt, soft tissue injuries of the limbs are to be randomized to be treated with Esflurbiprofen Hydrogel Patch or placebo (assumes a drop-out-rate of $\leq 10\%$).

The study will be performed in Germany in 3 sites. Each site should enroll a minimum of 30 and a maximum of 90 patients.

The first five doses of study drug will be applied at the study site. The patients will be instructed on how to apply the patch once daily at home for the last two treatment days.

After the randomization visit (V1), patients will return to the study center for post-baseline visits V2-V7 to complete efficacy and safety assessments. In addition, patients will assess pain on movement and spontaneous pain intensity at rest at visits 2, 3, 4, 5, 6 and 7.

The schedule of visits is described below.

	Time after initiating treatment	Visit Day
Randomization/Baseline visit V1	0 h	Day 1
1st interim visit V2	12 h (□ 1 h) after V1	Day 1
2nd interim visit V3	24 h (□ 2 h) after V1	Day 2
3rd interim visit V4	48 h (□ 4 h) after V1	Day 3

Table 4–1: Study site visits

Teikoku Chemical Co. Ltd Clinical Study Protocol : TK-254R-0201 Confidential Final Version 3.0

4th interim visit V5	72h (□ 4 h) after V1	Day 4
5th interim visit V6	96 h (□ 4 h) after V1	Day 5
Final visit V7	168 h (□ 24 h) after V1	Day 8 🗆 2day

Rescue medication (paracetamol, 500 mg tablets, up to 3000 mg daily) is allowed during the study, except for the 6 hours prior to V5 (72h).

5 Population

The study population will consist of male or female patients aged 18-60 years with blunt, soft tissue injuries of the limbs.

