6.5.4 Instructions for prescribing and taking the study drug

All patients will be treated with 1 patch of study drug at every visit during the first 6 visits (except for visit 2). The first five patches will be applied at the study center. The site of the first application will be marked with a water-resistant pen to ensure the same application site at every treatment. Additional 3 patches will be dispensed at Visit 6. The patients will be instructed to apply one patch every day at approx. the same time. Dosing times should be distributed as evenly as possible, preferably once every 24 hours after the last application.

Patients can take a shower or bathe prior to the application.

The Investigator or study staff will instruct the patients to apply the study drug exactly as prescribed and state that compliance is necessary for the patients' safety and the validity of the study. The patients will be told to contact the Investigator or study staff if they are unable for any reason to apply the patch as prescribed. All dosages prescribed and dispensed to the patient

and all dose changes during the study must be recorded on the Dosage Administration Record CRF page.

If the hydrogel patch begins to peel-off (>10% of the total surface), the edges of the topical system may be pressed down. If problems with adhesion persist, patients may overlay the topical system with a mesh netting sleeve, where appropriate (e.g., to secure topical systems applied to ankles, knees, or elbows). The mesh netting sleeve must allow air to pass through and not be occlusive (non-breathable)

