- □ Spontaneous pain intensity, pain at rest (PAR) (section 7.5.1)
- \Box Injury site pain-on-movement (POM) (section 7.5.1).
- \Box Global efficacy assessments (GEA) by patient and investigator (section 7.5.1).
- □ Responder rate 2 (number of patients able to resume training/ normal physical activity)
- \Box Adhesive power of patch (section 7.5.1)
- □ Local tolerability assessment.
- □ Collect remaining unused study drug and rescue medication.
- \Box Collect diary.
- □ Review diary
 - o Review the time and date of each patch application.
 - o Review rescue medication use. Count and document remaining rescue medication; (section 6.5.5).
- □ Perform a brief, general physical examination including vital signs and weight (section 7.6.1, 7.6.2). Urine dipstick pregnancy test (WOCBP and postmenopausal women who are not surgically sterile only) (section 7.6.4).
- \square Record changes in the use of concomitant medication (section 6.5.6).
- \Box Record information on AEs (section 8.1).
- □ Investigator evaluates whether the soft tissue injury/contusion has resolved and, if resolved, records the day and time it resolved.

Confidential Final Version 3.0

Table 7-1: Assessment schedule

8	Randomization visit (V1)	V2	V3	V4	V5	V6	Final visit ³ (V7)
Day	1	1 or 2	2	3	4	5	7, 8 or 9
Time after 1 st treatment	Oh	12h (±1)	24h (±2)	48h (±4)	72h (±4)	96h(±4)	7d (± 2d)
Written informed consent	X						
Inclusion / exclusion criteria	X						2
Demography / Med history	X						
Physical Exam / Vital Signs	X						X
Urine pregnancy test ¹	X						х
Concomitant medication	х	X	X	х	X	X	х
Injury site pain-at-rest (PAR)	X	X	X	х	X	X	х
Exam of soft tissue injury / contusion	х						х
Patch adhesion		X	X	Х	X	X	х
Local Tolerability assessment			X	х	X	X	х
Injury site pain-on-movement (POM)	х	x	x	x	x	x	х
Randomization	х						
Dispense IMP (patches) ²	х					x	
Dispense/Collect diary						X	х
Apply IMP (patch) at clinic	x		x	х	X	x	
Dispense rescue medication	X						
Count used/unused patches		X	X	х	X	X	х
Collect used IMP (patches)		x	x	x	x	x	х
Count rescue medication / Check time of intake		x	x	х	x	X	x
Adverse events		X	X	х	x	X	х
Global efficacy assessments				X	X		х
Collect rescue medication							X
Dispense three patches						X	

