¹ Female patients only; ² Patients will be given pouch containing IMP to take home in case of need to replace a detached patch. Patients bring IMP with them to each subsequent clinic visit. Patient apply patches themselves at 120h and 144h. ³ A final visit will be							

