9.6 Treatments (study drug, rescue medication, other concomitant therapies, compliance)

Compliance is defined in terms of the total number of study medication patches used and total number of applications made through Visit 7 as follows:

- \Box Good: \Box 80% of the patch has been applied and > 80% of scheduled applications made,
- $\hfill\square$ Moderate: not Good and not Poor
- \square Poor: < 50% of the patch has been applied or < 50% of scheduled applications made.

Compliance in patients with missing data on patch counts will be documented in the SAP before unblinding.

The % of patch used through Visit 7 will be computed relative to the actual number of applications made from randomization through Visit 7. Scheduled applications will include all scheduled applications through Visit 7.

Compliance will be summarized descriptively as (1) % of scheduled applications made, (2) % of patches used relative to number of actual applications and (3) compliance category (Good/Moderate/Poor).

Use of concomitant therapies will be listed. Use of rescue medication is an efficacy outcome and is discussed further below. Exposure to study drug will be summarized descriptively as (1) number of applications made and (2) total amount of patch used.

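### Protocol 7.5.1 times injury resolution by the last patch, but dosing is not tied to healing: course completers get no value or about 144 h, although Visit 7 records the actual day and time

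*Protocol*

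**What the plan says.** **The event-time rule.** Under the resolution heading of Protocol 7.5.1, the investigator judges at the final visit whether the injury has resolved. The time is then set by this sentence: "Time to resolution is the time of last application of study medication because the soft tissue injury/contusion has resolved". The next sentence bases it on the application record and the efficacy assessments. The resolution date entered at Visit 7 is not named.

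**The regimen.** The Synopsis (Dosage) has one patch "applied topically to the injured site once a day for 7 days". Protocol 6.5.4 gives every patient a clinic patch at Visits 1 and 3 to 6 and tells them to go on applying one a day. Footnote 2 of Table 7-1 adds: "Patient apply patches themselves at 120h and 144h". Protocol 6.5.9, on stopping study drug, does not list healing as a reason.

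**The other source.** In Protocol Section 7, the Visit 7 list reads: "Investigator evaluates whether the soft tissue injury/contusion has resolved and, if resolved, records the day and time it resolved".

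**What is done with the variable.** Protocol 9.7.3 and SAP 14.9 carry the same censoring rule: the day of the final visit, or 7 days after discontinuation for lack of efficacy. SAP 5.4 (derived variables) does not define the event time. The outcome lists in Protocol 9.7.1 and SAP 5.1.2 and 14.4.2 do not include it. They do list time to complete resolution of pain, but that is derived from the pain-on-movement VAS and is a different variable.

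**The concern.** A last-patch rule can date healing only if healing ends dosing. Here dosing is set by the calendar, so a patient who does as told has a last patch whose timing says nothing about the injury. The protocol thus holds two possible times for the same event and ties the definition to the less informative one.

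The SAP keeps a censoring rule but no event-time definition, so a programmer asked for this variable would go back to Protocol 7.5.1. At stake is whether one efficacy variable means what its name says, not the main conclusion of the trial.

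**Working it through.** **Inputs**
- Clinic patches at 0, 24, 48, 72 and 96 h (Protocol 6.5.4 and Table 7-1, Visits 1 and 3 to 6).
- Home patches at 120 and 144 h (Table 7-1, footnote 2).
- Visit 6 window of ±4 h (Protocol Section 4).

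**Step 1: when is the last patch?** 5 + 2 = 7 patches, which agrees with the seven-patch maximum in Protocol Section 4. The last is at 144 h. If the Visit 6 patch falls at 92 to 100 h and the next two follow at 24 h steps, the last is at 92 + 48 = 140 h to 100 + 48 = 148 h.

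**Step 2: apply Protocol 7.5.1 to a resolved patient who completes the course.**
- *Strict reading.* The last patch must be the last because the injury has resolved. For this patient it was the last because the course ended. No application qualifies, and there is no value.
- *Looser reading.* Ignore the reason and take the last patch. The value is about 144 h regardless of healing time, and the error is 144 minus the healing time:

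| Healed at (h) | Value (h) | Error (h) |
|---|---|---|
| 24 | 144 | +120 |
| 48 | 144 | +96 |
| 72 | 144 | +72 |
| 96 | 144 | +48 |
| 120 | 144 | +24 |
| 144 | 144 | 0 |
| 160 | 144 | −16 |

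These errors belong to the looser reading only. The strict reading has no error to compute because it yields no time.

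**Step 3: apply it to a patient who stops on healing.** The last patch precedes healing by less than one 24 h dosing interval if healing occurs by 168 h. For example, healing at 60 h gives 48 h, an error of −12 h. For such patients the rule is usable.

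**Step 4: does any text tell patients to stop?** The Synopsis, Protocol 6.5.4 and Table 7-1 all prescribe continuing, and Protocol 6.5.9 does not mention healing. The compliance denominator in Protocol 9.6 makes no exception for healed patients: "Scheduled applications will include all scheduled applications through Visit 7". Stopping after 1, 2 or 3 of 7 patches is 14.3%, 28.6% or 42.9% of schedule, which is Poor (below 50%). Stopping after 4 or 5 is 57.1% or 71.4%, which is at best Moderate. Stopping after 6 is 85.7%, above the 80% line.

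**The case against.** **The authors may have meant patients to stop on healing.** Protocol Section 2 says dosing goes on through resolution of the injury, Section 4 speaks of up to 8 days, and SAP 4.1.2 of up to seven days. If dosing did end at healing, the rule would work to within a dosing interval (Step 3). This stands in part: the texts leave room for early stopping. But they are rationale and design summary, not instruction. Section 2 also gives its aim as assessing safety over the whole dosing interval, which points as much to completing the course.

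**Protocol 7.5.1 does not rest on the patch record alone.** It also names the efficacy assessments. That is correct, so a reader who infers that every completer would certainly be recorded at 144 h goes too far. How the assessments would change the time is not stated, however, so the gap remains.

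**The compliance rule is weak evidence.** The categories are only summarised descriptively, and the per-protocol definition in SAP 14.2 does not name them. They show that the plan expects all seven patches, but not that patients are penalised for stopping. The dosing text carries the point without them.

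**Little is lost.** The Visit 7 date is collected whatever Protocol 7.5.1 says. This stands, and it limits the severity.

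**Conclusion.** The inconsistency is real and minor. For resolved patients who complete the seven-patch course, Protocol 7.5.1 gives either no time or about 144 h whatever the healing time, while a direct record of that time exists at Visit 7. The conclusion rests on the dosing text as written. It does not extend to patients who in fact stopped on healing, and the documents do not say how many would.

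A reader might infer that a treatment comparison of healing times would lose power. The documents do not support a figure for that. Protocol 9.7.2 and SAP 14.4.2 give a center-stratified log-rank test for time-to-event outcomes, but this variable is on no outcome list, so a test of it is not a stated commitment. Neither document gives a healing distribution or an expected effect on healing. The primary endpoint at 72 h, the listed secondary endpoints and the sample size are unaffected.

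**What to change.** 1. In SAP 5.4, before unblinding, define time to injury resolution as the resolution day and time recorded by the investigator at Visit 7 minus the day and time of the first patch. Record it as a change from Protocol 7.5.1.
2. Keep the censoring rules in SAP 14.9 as they are.
3. List the variable as exploratory in SAP 14.4.3. If it will not be analysed, delete its line in SAP 14.9 instead.

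**Cost.** By the SAP route this is wording only: SAP Section 1 has the plan finalised after the blind review meeting, and the date is already collected. Changing Protocol 7.5.1 itself would need a written amendment with the approvals in Protocol 11.1.

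**Downside.** The recorded date is partly recalled. Table 7-1 schedules an examination of the injury only at Visits 1 and 7, so healing in between is dated in retrospect. A date with recall error is still more informative than a constant or a missing value.

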7.5.2 Appropriateness of efficacy measurements

The efficacy outcomes selected are standard for this indication.

7.6 Safety

7.6.1 Physical examination

A brief, general physical examination will be performed at Visit 1 (randomization visit) and at Visit 7 (study termination - final visit), as well as when judged necessary by the Investigator. Examination will include: general condition, dermatologic, eyes, ears, nose, throat, neck, thyroid, heart, respiratory system, abdomen, kidneys, skeletal system, extremities, lymphatic system, CNS, neurological conditions according to the state of the art.

